5.6.1.1 COVID-19 Vaccination

Various guidelines (eg, NCCN Guidelines: Cancer and COVID-19 Vaccination [NCCN 2021] and MHRA Guidance on Coronavirus [COVID-19] [MHRA 2021]) have noted that COVID-19 vaccination should be prioritized for subjects with cancer with the understanding that there are limited safety and efficacy data in this subject group. These guidelines also state:

- “Delay of vaccination until immunosuppressive therapy is reduced and/or based on immunophenotyping of T cell and B cell immunity can be considered.”
- “Systemic corticosteroids and targeted agents are expected to blunt immune responses to vaccination.”

This study utilizes a mandatory premedication regimen that contains corticosteroids (ie, 20 mg of i.v. dexamethasone) for at least the duration of the first cycle (ie, Cycle 1). Therefore, **for new subjects to be enrolled in the study**, every effort should be made to vaccinate subjects prior to being considered for this study based on the Investigator's risk/benefit analysis for each subject. Any COVID-19 vaccination should be at least 2 weeks prior to C1D1; live attenuated vaccines at least 4 weeks prior to C1D1.

For subjects whose opportunity for COVID-19 vaccination arrives during the conduct of the study (ie, ongoing subjects in the study), the following should be noted:

- COVID-19 vaccination should be avoided during the DLT period or Cycle 1 of the study period.
- As stated in Section 5.3, Investigators may taper premedication with corticosteroids for those subjects who do not experience IRR/CRS symptoms Grade >1 during the previous infusion starting with the third subsequent infusion (C1D15 for weekly dosing schedule and C2D1 for q2w schedule).
- If the vaccination opportunity falls within the mandatory corticosteroid premedication period, there should be a consideration by the Investigator for holding or tapering the corticosteroid to prioritize vaccination on a case-by-case basis based on the risk/benefit analysis by the Investigator/treating MD.
- COVID-19 vaccination is not permitted on AFM24 dosing days. Vaccination should be administered at least 3 days before or 3 days after the AFM24 treatment administration day.
- It should be noted that no planned dose delays for study drugs are allowed during the DLT period (ie, Cycle 1).

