Diagnosis and Main Criteria	
Subjects will be considered eligible to be enrolled in the study if ALL of the inclusion criteria and NONE of the exclusion criteria are met as defined below. Prospective approval of protocol deviations to recruitment and enrollment criteria, also known as protocol waivers or exemptions, is not permitted.
 
Please note that based on various guidelines (e.g., NCCN Guidelines: Cancer and COVID-19 Vaccination Advisory Committee. Version 8.0; Jun 03, 2023 MHRA Guidance on Coronavirus [COVID-19] [MHRA 2021]), COVID-19 vaccination should be prioritized for subjects with cancer with the understanding that there are limited safety and efficacy data in this subject group. These guidelines also state:
 
• “Delay of vaccination until immunosuppressive therapy is reduced and/or based on immunophenotyping of T cell and B cell immunity can be considered.”• “Systemic corticosteroids and targeted agents are expected to blunt immune responses to vaccination.” 
This study utilizes a mandatory premedication regimen that contains corticosteroids (i.e., 20 mg of i.v. dexamethasone) for at least the duration of the first cycle (i.e., Cycle 1). Therefore, for any new subjects to be enrolled in the study, every effort should be made to vaccinate subjects prior to being considered for this study based on the Investigator’s risk/benefit analysis for each subject. Any COVID-19 vaccination should be at least 2 weeks prior to C1D1; live attenuated vaccines at least 4 weeks prior to C1D1. For subjects whose opportunity for COVID-19 vaccination arrives during the conduct of the study (i.e., ongoing subjects in the study), see instructions for COVID-19 vaccination provided in Section 5.6.1.1.
 
INCLUSION CRITERIA
 
The study will enroll subjects with advanced or metastatic solid malignancies whose disease has progressed after treatment with previous anticancer therapies.
 
Subjects are eligible only if all the following criteria are met:
 
1) For the dose escalation phase (Phase 1): histologically or cytologically confirmed advanced or metastatic solid malignancies that are known to express EGFR. For the dose expansion phase (Phase 2a): histologically or cytologically confirmed advanced or metastatic EGFR⁺ malignancies. EGFR expression is defined as positive staining for EGFR in ≥1% of tumor cells determined by a validated immunohistochemistry assay. Archived paraffin embedded tumor tissue is acceptable for EGFR determination— otherwise a fresh tumor biopsy must be performed. Local laboratory EGFR assessment is acceptable.2) For dose escalation phase (Phase 1): Subjects must have been previously treated with 1 or more lines of anticancer therapy and have documented disease progression during or after their most recent line of anticancer therapy. In addition, either there is no further SOC therapy for the subject or the remaining SOC therapies are deemed not appropriate for the subject by the Investigator.3) Subjects must have documented radiological progression during or after their latest therapy for all phases.4) Voluntary provision and understanding of signed and dated, written informed consent prior to any mandatory study-specific procedures, sampling, or analysis.

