4.0 SELECTION AND WITHDRAWAL OF SUBJECTS

Subjects will be considered eligible to be enrolled in the study if ALL the inclusion criteria and NONE of the exclusion criteria are met as defined below.

Prospective approval of protocol deviations to recruitment and enrollment criteria, also known as protocol waivers or exemptions, is not permitted. Please note that based on various guidelines (eg, *NCCN Guidelines: Cancer and COVID-19 Vaccination* [NCCN 2021] and *MHRA Guidance on Coronavirus [COVID-19]* [MHRA 2021]), COVID-19 vaccination should be prioritized for subjects with cancer with the understanding that there are limited safety and efficacy data in this subject group. These guidelines also state:

- “Delay of vaccination until immunosuppressive therapy is reduced and/or based on immunophenotyping of T cell and B cell immunity can be considered.”
- “Systemic corticosteroids and targeted agents are expected to blunt immune responses to vaccination.”

This study utilizes a mandatory premedication regimen that contains corticosteroids for at least the duration of the first cycle (ie, Cycle 1). **Therefore, for any new subjects to be enrolled in the study**, every effort should be made to vaccinate subjects prior to being considered for this study based on the Investigator’s risk/benefit analysis for each subject. Any COVID-19 vaccination should be at least 2 weeks prior to C1D1; live attenuated vaccines at least 4 weeks prior to C1D1. **For subjects whose opportunity for COVID-19 vaccination arrives during the conduct of the study (ie, ongoing subjects in the study)**, see instructions for COVID-19 vaccination provided in Section 5.6.1.1.

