5.3 Premedication Regimen and Post-Dose Observation

Subjects are required to receive premedication with the following medications approximately 1 hour before each dose of AFM24:

- i.v dexamethasone 20 mg (or equivalent long-lasting steroid dose)
- i.v. H1 antagonist (e.g., diphenhydramine 50 mg or similar medication as used per local institutional practice) with or without an H2 antagonist (e.g., famotidine or similar medication as used per local institutional practice), and
- acetaminophen dosage as per local institutional practice (e.g., 650 mg to 1000 mg or equivalent).

Note: For infusion times that span over 2 days (i.e., split day dosing), subjects must receive premedication on Day 1 and as well on Day 2. This includes the H1 antagonist (with or without an H2 antagonist), acetaminophen, and dexamethasone. For Day 2, dexamethasone dose can be reduced to a minimum of 8 mg, according to local standards at the discretion of the Investigator/treating physician.

Subjects may also be administered prophylactic antiemetic medications as indicated. Additional oral premedication will be allowed on the day before each dose of AFM24 at the discretion of the Investigator, in particular for those subjects who may experience persistent IRR.

If the first 2 subsequent infusions are well tolerated (defined as no Grade >1 IRR/CRS), then the medication(s) within the premedication regimen can be tapered/decreased.

Clinicians should be prepared for an IRR or CRS to occur during or shortly after each AFM24 drug administration, with frequent monitoring of vital signs and medical equipment and supplies readily available and standing orders in place for immediate intervention. Please see APPENDIX F (Section [14.6](#)) for details regarding treatment management for symptoms of IRR/CRS due to study drug.

After the first 2 subsequent doses of AFM24 subjects must be observed for at least 4 hours after the end of infusion (EOI), with regular checks of vital signs as described in Section [7.2.4](#).

In case of a split day dosing (over 2 days) subjects must be observed for at least 4 hours after the end of AFM24 infusion on each day. In this scenario, the split day dosing AFM24 infusion is considered 1 dose. If no signs or symptoms of CRS or an IRR (no Grade >1) are observed during or after the first 2 subsequent doses of AFM24 then the observation period following each AFM24 dose may be reduced from 4 hours to at least 2 hours after the end of infusion.

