In addition, pre-medication with steroids, antihistamines, and oral acetaminophen is advised to minimize the severity of IRR/CRS (see Section 5.3). Other premedication such as antiemetics (e.g., ondansetron, metoclopramide hydrochloride) may be administered at the discretion of the Investigator/ treating physician.

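### The protocol makes 20 mg dexamethasone premedication mandatory for at least all of Cycle 1, yet allows a steroid taper from C1D15 on the weekly schedule, under differently worded triggers

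*Protocol*

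**What the plan says.** **Mandatory through Cycle 1.** The synopsis eligibility text describes a mandatory regimen with "corticosteroids (i.e., 20 mg of i.v. dexamethasone) for at least the duration of the first cycle". Section 5.6.1.1 says that the regimen "contains corticosteroids (ie, 20 mg of i.v. dexamethasone) for at least the duration of the first cycle". Section 4.0 refers to a "mandatory premedication regimen that contains corticosteroids for at least the duration of the first cycle" and names no dose.

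**Taper allowed within Cycle 1.** Section 5.3 opens with a firm rule: "Subjects are required to receive premedication with the following medications approximately 1 hour before each dose of AFM24". It then relaxes it: "If the first 2 subsequent infusions are well tolerated (defined as no Grade >1 IRR/CRS), then the medication(s) within the premedication regimen can be tapered/decreased". Section 5.2 and the synopsis dosing text attach the same two-infusion condition to a package of possible changes (shorter infusion, shorter observation, steroid taper). They date the earliest change to the third infusion: C1D15 on the weekly schedule and C2D1 on the q2w schedule. They allow only one such change per infusion.

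**A second and third trigger.** Section 5.6.1.1, citing Section 5.3, says "Investigators may taper premedication with corticosteroids for those subjects who do not experience IRR/CRS symptoms Grade >1 during the previous infusion", again from C1D15 on the weekly schedule. Appendix F (Section 14.6.1) also starts at C1D15 but refers to the previous infusions in the plural.

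**Status of the premedication.** Section 5.3 requires it. The introduction to Appendix F, pointing back to Section 5.3, says that premedication with steroids, "antihistamines, and oral acetaminophen is advised to minimize the severity of IRR/CRS".

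**DLT window.** Section 3.4 sets it as the first 4-week cycle, and Phase 1 dosing is weekly only (Section 5.2). The SAP repeats the DLT rules in Section 7.7.1 and says nothing on premedication.

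**The concern.** A site can follow the protocol in good faith and reach opposite answers on whether the steroid dose may be reduced at C1D15 or C1D22. Section 5.6.1.1 contains both answers. A site that relies on the triggers can also reach different answers for the same patient, depending on which section it reads.

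This matters because IRR/CRS is both the expected toxicity and a route to a DLT. Table 3 counts a Grade 4 IRR/CRS as a DLT, and also a Grade 3 IRR/CRS that does not improve to Grade 2 or better within 6 hours. Steroid premedication is given to limit exactly these events. If steroid cover in the DLT window depends on the page a site reads, conditions are not uniform among subjects at the same AFM24 dose, and it is unclear what counts as a protocol deviation.

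**Working it through.** No sample size, power or error rate is involved. The check counts the doses exposed to the conflict, then sets the rules side by side for each possible reaction history.

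**Doses exposed.** Weekly Cycle 1 doses fall on D1, D8, D15 and D22 (Section 5.2), and the earliest taper is at the third infusion, D15. Doses on or after D15: 2 of 4. On the q2w schedule the Cycle 1 doses are D1 and D15 and the earliest taper is C2D1, so 0 of 2 are exposed; q2w is in any case a Phase 2a option with no DLT window.

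**May the steroid be tapered at C1D15?** A plus marks a Grade >1 IRR/CRS after which dosing continued; a minus marks none.

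| C1D1 | C1D8 | Mandatory text (synopsis, 5.6.1.1) | First two infusions (synopsis dosing, 5.2, 5.3) | Previous infusion (5.6.1.1) | Previous infusions, read as all (App. F) |
|---|---|---|---|---|---|
| − | − | No | Yes | Yes | Yes |
| − | + | No | No | No | No |
| + | − | No | No | **Yes** | No |
| + | + | No | No | No | No |

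The table shows two separate defects:

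- In the first row every trigger permits a taper and the mandatory text does not. This is the main contradiction, and it concerns subjects who tolerated both infusions.
- In the third row the triggers themselves disagree. That is 1 of 4 histories.

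**At C1D22** there are 2 × 2 × 2 = 8 histories over D1, D8 and D15. Read Section 5.3 literally, as looking only at the first two infusions, and compare it with the previous-infusion wording. They differ in 4 of 8: (−,−,+), (−,+,−), (+,−,−) and (+,+,−). In the first of these the literal Section 5.3 text would allow a taper straight after a Grade >1 reaction at D15; in the other three only the Section 5.6.1.1 wording allows it.

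These are counts of patterns, not probabilities. The documents give no Grade >1 IRR rate by infusion and no frequency of tapering.

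**What the escalation figures can and cannot show.** In Table 19, 0/3 DLTs at 120 mg permits 360 mg (scenario 8), while 1/3 keeps the next cohort at 120 mg (scenario 9a). Recomputing with the Table 8 prior, d* = 180 mg and 0/2 at both 14 mg and 40 mg gives an overdose probability at 360 mg of 0.236 after 0/3 (Table 19 prints 0.245) and 0.544 after 1/3, against the 0.25 limit. So one DLT is decisive at that step. The calculation contains no information on premedication and does not measure this problem.

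**The case against.** The best defence is that the operative rule is nearly uniform. Premedication is governed by Section 5.3, with timing in Section 5.2, and the statement about all of Cycle 1 appears only as background to vaccination advice. Section 4.0 gives no dose, so a tapered regimen is compatible with it. The singular noun in Section 5.6.1.1 sits in a sentence that cites Section 5.3 and looks like a slip of paraphrase. Two related oddities have harmless readings. Appendix F uses a softer verb but refers back to Section 5.3. The advice to consider holding the steroid for vaccination need not clash with avoiding vaccination in Cycle 1, because a mandatory period of at least Cycle 1 can run longer.

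Much of this stands, and it explains how the text arose. It does not remove the contradiction: the synopsis and Section 5.6.1.1 attach a specific 20 mg dose to a regimen they call mandatory for at least Cycle 1, and a taper from C1D15 cannot satisfy that. A reader of Section 5.6.1.1 alone would apply the wrong trigger if Section 5.3 governs.

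A reader might infer more: that uneven steroid cover has distorted the DLT data and that the BLRM, with dose as its only covariate, has read this as a dose effect. The documents do not support that, for these reasons:

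- Section 8.3.1 says that most IRRs come with the first infusion, before any taper.
- Only a narrow class of IRR/CRS counts as a DLT.
- Confusion with dose would need tapering to vary with dose, and nothing shows that it did.
- Escalation also rests on SRC review of all data, not on the model alone (Sections 3.4 and 9.3.4.1).
- The 69% IRR figure in Section 1.6 is not split by grade or infusion, and the same section reports no DLTs in 6 subjects at 480 mg.

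It would equally be too strong to say that half of all Cycle 1 doses were affected. Two of four is a count of scheduled slots.

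**Conclusion.** The contradiction is real and wrong as written. The protocol gives incompatible instructions on whether the steroid dose may be reduced at C1D15 and C1D22, and it words the condition for a taper in three ways.

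Its reach is limited. It affects weekly dosing only, and a dose is affected only when the investigator elects to taper; the one-change-per-infusion rule may push that from C1D15 to C1D22. At C1D15 the trigger wordings separate only for a subject with a Grade >1 reaction on C1D1 and none on C1D8. The effect on DLT counts or dose decisions cannot be sized and should not be described as a demonstrated bias.

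The conclusion assumes that the stated 20 mg is part of the mandatory requirement, as the synopsis and Section 5.6.1.1 word it, and that Appendix F's plural means all earlier infusions. Prospective benefit is modest: an RP2D had been selected (Section 1.6), and enrolment has been stopped in the three expansion cohorts (Sections 3.8 and 9.3.8.2). The edit still matters for any subject yet to enter Cycle 1 and for classifying deviations.

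**What to change.** Reconcile the synopsis eligibility text, Section 4.0 and Section 5.6.1.1 with the synopsis dosing text, Sections 5.2 and 5.3, and Appendix F. The protocol should:

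1. State once, with cross-references elsewhere, whether Cycle 1 steroid premedication may be tapered within the DLT window.
2. Use one trigger wording throughout, worded so that it also gives a single answer at C1D22 after a reaction at C1D15.
3. Use the same verb for premedication in Section 5.3 and in the introduction to Appendix F.

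Which rule applies is the sponsor's decision. The cost is a wording edit in an amendment.

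Optionally, show the steroid dose given and the infusion duration beside each Cycle 1 IRR/CRS event in the planned DLT and AE listings (SAP Sections 7.7.1 and 7.8.2). The SAP describes no listing that links the two. Concomitant medication dose and date are already recorded in the eCRF (Section 5.6.1), so this needs programming only. It would let a reader see whether any reaction occurred under reduced cover.

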5.6.2 Prohibited Concomitant Medications

Medications specifically prohibited in the exclusion criteria are not allowed during the ongoing study. If there is a clinical indication for any medication specifically prohibited during the study, discontinuation from study drug may be required. The Investigator should discuss any questions regarding this with the Sponsor. The final decision on any supportive therapy rests with the Investigator and/or the subject's primary physician. However, in such cases, the decision to continue the subject on AFM24 study drug requires the mutual agreement of the Investigator, Sponsor, and subject.

Apart from the exceptions listed in the inclusion/exclusion criteria, subjects are prohibited from receiving the following therapies during the Screening (see Exclusion Criteria Section 4.2) and Treatment periods of this study, with exception of the treatment of AEs occurring during the study:

- Antineoplastic systemic chemotherapy or biological therapy;
 - Exceptions: LHRH agonists/antagonists, bisphosphonates, and RANK ligand inhibitors will only be allowed during the study provided that the treatment was started prior to the study and the subject has been on a stable dose for at least 3 months (i.e., ≥ 3 months) from first day of study drug. Additionally, LHRH agonists should not be discontinued during the study.
- Immunotherapy not specified in this protocol;
- Investigational agents other than AFM24;
- Radiation therapy;
- Immunosuppressant drugs such as systemic glucocorticoids (high-dose steroids defined as ≥ 10 mg prednisone or equivalent per day, exceptions see below), Janus kinase inhibitors (e.g., tofacitinib), calcineurin inhibitors (e.g., cyclosporine), mTOR inhibitors (e.g., sirolimus), IMDH inhibitors (e.g., azathioprine), biologics (e.g.,

etanercept), monoclonal antibodies (e.g., infliximab);

- Systemic glucocorticoids for any purpose other than to prevent IRR/CRS and/or to modulate symptoms from an AE of suspected immunological etiology.

Exceptions:

- Topical ($\leq 20\%$ of the skin surface area), ocular, intra-articular, intranasal, or inhalation corticosteroids with minimal systemic absorption
- A short course (≤ 7 days) of corticosteroids prescribed prophylactically (e.g., for contrast dye allergy or antiemetic therapy) or for treatment of non-autoimmune causes (e.g., delayed hypersensitivity reaction caused by contact allergen)
- Physiological replacement doses of corticosteroids for adrenal or pituitary insufficiency
- Corticosteroid use for the management of symptoms of IRR/CRS is permitted

Subjects who, in the assessment by the Investigator, require the use of any of the aforementioned treatments for clinical management should be removed from the study. Subjects may receive other medications that the Investigator deems to be medically necessary.

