3.9 Period of Observation

After completion of study drug, subjects will enter follow-up and will be contacted regularly by the Investigator or study personnel to collect information about subsequent therapies, disease status, and survival. Subjects will be followed for safety, duration of response (DOR), progression free survival (PFS), and overall survival (OS) until the end of the study, (see below).

Observation Visits:

- End of Treatment visit: Visit to be performed 14 days (± 2 days) from last drug intake or before start of any new anti-cancer treatment whichever is sooner. For subjects who discontinue prematurely before disease progression it must be performed as the last visit.
- Safety Follow Up visit: All subjects will undergo one Safety Follow-up visit 30 days (± 5 days) after the last AFM24 infusion or before start of any new anti-cancer treatment whichever is sooner.
- Long-term Follow Up: Additional follow-up (phone contact) will take place at 3-month intervals (± 2 weeks) after end of treatment visit until death, lost to follow-up- or mutual decision between PI and sponsor to discontinue Long-term Follow Up of the patient, whichever is sooner.
- End of Study: The study will be terminated as soon as all subjects have completed the first Long-term Follow-Up interval, withdrawn, or died, whichever occurs first.

The study will be analyzed and reported once the last subject of the study has experienced at least one of the following:

- Has been treated till at least 4 weeks after the 1st post-baseline tumor assessment
- Disease progression
- Withdrawal from treatment due to a drug related AE
- Fatal event
- Lost to Long-term Follow-Up
- Withdrawal of consent
- Start of other anti-cancer treatment

In case subjects are still being treated with study medication at the primary analysis cut-off date for this study, such subjects will be kept on treatment in the study and data collected will then be reported in an addendum to the final clinical study report (CSR). It will be noted in the final CSR that such a revised report may be provided.

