4.3 Subject Withdrawal from Study

Throughout the study, treatment with AFM24 may continue until the occurrence of 1 of the following events, whichever comes first:

- Subject withdrawal of consent;
- Disease progression (if initial radiological progressive disease is observed, while the clinical condition of the subject is stable, treatment continuation is allowed at the discretion of the Investigator. If treatment is continued after initial progressive disease, a confirmatory scan should be acquired within 4 to 6 weeks);
- Occurrence of intolerable toxicity;
- DLT during Cycle 1 in the Phase 1 part;
- Subject non-compliance and the need for withdrawal for this reason as assessed by the Investigator; or
- Investigator decision that it is in the subject's best interest to withdraw from the study.

Upon withdrawal from study drug, the reason for withdrawal should be sought and recorded in the subject file and the withdrawal will be captured in the electronic case report form (eCRF). Every effort will be made to complete the End of Treatment visit, the Safety Follow-up visit and for the subject to be followed up every 3 months thereafter. Where a subject withdraws his/her consent to participate in the study, such follow-up assessments cannot be conducted. The management and holding of data around subject withdrawal will be described in the subject ICF.

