9.3.5 Secondary Analyses

9.3.5.1 Phase 1 (Dose Escalation) & Phase 2a (Dose Expansion)

9.3.5.1.1 Efficacy Analyses

All efficacy analyses will be done for Investigator assessed RECIST v1.1 ([Eisenhauer et al., 2009](#); [Schwartz et al., 2016](#)), Investigator assessed iRECIST ([Seymour et al., 2017](#)), Central assessed RECIST v1.1 and Central assessed iRECIST. The local Investigator assessed RECIST is the primary endpoint for the Phase 2a.

9.3.5.1.1.1 Overall Response Rate

Overall response as defined by achieving confirmed CR and/or PR assessed by RECIST v1.1 will be presented by percentage rates and where appropriate the 95% confidence intervals (CIs). Partial or complete response needs to be confirmed with repeated assessment at least 4 weeks after the initial assessment. For changes in solid tumor size waterfall plots will be presented. For all response assessments swimmer plots will be presented. All response assessments will be listed.

9.3.5.1.1.2 Disease Control Rate at Month 3, 6, and 9

Disease control at months 3, 6, and 9, as defined by achieving CR and/or PR and/or SD assessed by RECIST v1.1 will be presented by percentage rates and where appropriate the 95% CIs. Waterfall plots will be presented.

9.3.5.1.1.3 Duration of Response

The DOR defined as time from first assessment of PR or CR to follow-on first assessment of progressive disease will be summarized by descriptive statistics including median DOR and where appropriate the respective 95% CIs. DOR will also be listed.

9.3.5.1.1.4 Progression Free Survival and Overall Survival

Time from first treatment received until disease progression or OS will be summarized by Kaplan-Meier estimates, median PFS/OS and where appropriate the respective 95% CIs. Subjects with no event will be censored at the last available tumor assessment for PFS and at the last timepoint known alive for OS.

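### Section 5.6.2 gives two incompatible consequences for needing a prohibited treatment, and its closing sentence, read literally, could cut off survival follow-up

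*Protocol*

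**What the plan says.** Protocol Section 5.6.2 deals twice with a subject who comes to need a prohibited treatment.

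- The opening paragraph speaks of study drug and is conditional: "discontinuation from study drug may be required". It then provides a route to stay on treatment: "the decision to continue the subject on AFM24 study drug requires the mutual agreement of the Investigator, Sponsor, and subject".
- The closing paragraph speaks of the study and offers no such route. Subjects who, in the investigator's assessment, "require the use of any of the aforementioned treatments for clinical management should be removed from the study".

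The list between the two covers antineoplastic and biological therapy, other immunotherapy, other investigational agents, radiation, immunosuppressants and systemic glucocorticoids. It applies during Screening and Treatment, "with exception of the treatment of AEs occurring during the study", and has named exceptions.

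Follow-up is set out elsewhere. Section 3.9 follows subjects after treatment for safety, duration of response, "progression free survival (PFS), and overall survival (OS) until the end of the study". Section 4.3 says that, after withdrawal from study drug, every effort will be made to complete the End of Treatment and Safety Follow-up visits and "for the subject to be followed up every 3 months thereafter". The obstacle it names is loss of consent: "Where a subject withdraws his/her consent to participate in the study, such follow-up assessments cannot be conducted". Protocol Section 9.3.5.1.1.4 censors subjects without an event "at the last timepoint known alive for OS", and the SAP (Section 7.7.3) uses the latest available observed date.

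**The concern.** Two things are at stake. First, a site facing this situation has two instructions that lead to different actions on AFM24, so sites may handle like subjects differently.

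Second, the closing sentence names the study, not the study drug. If a site acts on that wording, the subject leaves follow-up and OS is censored at removal. Needing other anticancer therapy, radiation or immunosuppressive doses of steroid plausibly marks worsening disease, so the censoring would be informative. OS is a Phase 2a secondary endpoint in protocol Table 2 and is summarised by Kaplan-Meier, which assumes that censored subjects have the same prognosis as those still observed.

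**Working it through.** The plan gives no figure on this point, so the check is a comparison of texts.

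**1. Does Section 5.6.2 agree with itself on AFM24?** The opening paragraph makes stopping possible but not automatic, and continuation possible by three-way agreement. The closing paragraph says the same subjects should be removed. If the three parties agree to continue, the two paragraphs give opposite answers. The conflict is real whatever is meant by removal.

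**2. Is study used as a synonym for study drug?** Not consistently.
- Separated: Section 9.2 summarises reasons for discontinuing the study and the study drug as two items; Section 4.4 speaks of withdrawal from treatment and/or the study.
- Blurred: Section 4.3 is titled as withdrawal from study, yet lists events that stop AFM24 and then describes follow-up after withdrawal from study drug.

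**3. What follows under each reading?**
- *Removal means stopping AFM24.* Section 4.3 applies, 3-monthly contact continues and OS is unaffected. Only the conflict in step 1 remains.
- *Removal means leaving the study.* Sections 3.9 and 3.11 count a withdrawn subject as finished without a Long-term Follow-Up interval, and OS is censored at the last date known alive. Let *w(t)* be the share of those alive at time *t* who have not been removed, with death hazard λ_R, and let λ_P be the hazard in those removed. The true hazard is w·λ_R + (1 − w)·λ_P. Kaplan-Meier sees only λ_R. The hazard it misses is (1 − w)(λ_P − λ_R), which is positive whenever removed subjects fare worse. Estimated survival is then too high.

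**4. Who is covered?** Only subjects still in Screening or Treatment, so therapy begun after AFM24 has stopped is outside the rule. Also outside are treatment of adverse events, the listed steroid exceptions (topical or local, short course, physiological replacement, management of infusion reactions or cytokine release) and palliative limited-field radiotherapy for pain from bone metastases present at baseline (exclusion criterion 3).

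**5. Which other endpoints move?**
- PFS and duration of response: the SAP table in Section 7.7.3 already censors at new anticancer therapy, so removal adds little there. It could add censoring for steroids or immunosuppressants. The SAP does not say whether radiotherapy counts as new anticancer therapy.
- Response rate: efficacy uses the safety set (protocol Section 9.1, SAP Section 6.1) and Phase 2a subjects are not replaced (protocol Section 3.4.4), so the denominator stays the same.

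**6. How large?** Neither document gives a rate of prohibited-treatment use or the survival of such subjects. The cohorts are small: in Cohort B, closed after 8 patients, one removed subject is 1/8 = 12.5%.

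**The case against.** The strongest case on the other side is that removal here is loose wording for stopping AFM24. Section 3.9 ends Long-term Follow Up at death, loss to follow-up or a joint decision of investigator and sponsor; a prohibited treatment is not on that list. Follow-up is meant to record subsequent therapies, and the schedules of assessments carry a row for subsequent treatments and survival, which would make little sense if another therapy ended follow-up. The closing sentence also says should, not must.

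Much of this stands. A reader might infer that the plan stops survival follow-up for every subject who needs a prohibited treatment. The documents do not say so; the weight of Sections 3.9 and 4.3 is against it. Nor does the opening paragraph simply let subjects continue, since all three parties must agree. A reader might also infer a general upward bias in PFS, or an effect on when the analyses are triggered. Step 5 answers the first in large part. On the second, starting other anticancer treatment is itself one of the reporting triggers in Section 3.9, so removal is not needed to set it off.

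What the objection does not answer is the conflict inside Section 5.6.2, or the fact that the literal wording, combined with the end-of-study definition, permits a site to close a subject's follow-up.

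**Conclusion.** The contradiction in Section 5.6.2 is established from the text. The risk to OS is conditional: it arises only if sites read the closing sentence literally, and the bias is upward only if the subjects removed have a worse prognosis than those who remain. Its size cannot be estimated from the documents.

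A reader might be tempted to attach a number. Assume a median OS of 8 months, 10% to 30% of subjects affected at a time *u* uniform over months 1 to 4, a hazard *h* = 2 to 3 times higher afterwards, and all of them lost. The Kaplan-Meier median stays at 8.0, and the true median solves (1 − f)e^(−λt) + f·E[e^(−λ(u + h(t − u)))] = 0.5 with λ = ln 2/8 = 0.0866.
- f = 0.1, h = 2: at t = 7.6, 0.9 × 0.518 + 0.1 × 0.334 = 0.50.
- f = 0.3, h = 3: at t = 6.24, 0.7 × 0.582 + 0.3 × 0.308 = 0.50.

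That is a gap of about 0.4 to 1.8 months. Every input is assumed, and loss of every such subject is the very point the documents leave open, so this is not an estimate for this trial. Under the same 8-month exponential with complete follow-up, the standard error of the median is about 1/(λ√n): 4.1 months at n = 8 and 3.0 at n = 15. Those sizes are Cohort B's closing number and the largest planned interim size; actual enrolment in Cohorts A and C is not given. OS here is descriptive, without a comparator. The point is worth correcting because correction is nearly free, not because a large bias has been shown.

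**What to change.** Two changes to protocol Section 5.6.2.

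1. Reconcile the opening and closing paragraphs on whether AFM24 may continue when a prohibited treatment is needed. Which rule applies is for the clinical team.
2. Add to the closing paragraph that, whatever is decided about study drug, these subjects complete the End of Treatment and Safety Follow-up visits and remain in Long-term Follow-Up for survival and subsequent therapy under Sections 3.9 and 4.3, unless consent is withdrawn.

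The cost is amended wording, plus phone contacts that the 3-monthly schedule already contains. The SAP's censoring rules need no change for this.
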